- 6. Tumor assessments will include contrast-enhanced computed tomography (CT) and/or magnetic resonance imaging (MRI) of the chest, abdomen, and pelvis as well as the site of the primary tumor (if applicable). Measurable lesions will be assessed at Screening and then every 8 weeks (±7 days) after Cycle 1, Day 1 for the first year; and every 12 weeks (±7 days) thereafter until disease progression or treatment discontinuation (whichever occurs last), initiation of a new line of therapy or death. Tumor assessments performed as standard of care prior to obtaining informed consent and within 28 days of Cycle 1, Day 1 may be used as the screening tumor assessment rather than repeating the scans. Evaluation of tumor response will be based on RECIST v1.1 criteria (see Appendix 7). Every time a tumor assessment is done, a PD Serum sample should be collected.

Table 1 Schedule of Activities: Q2W regimen for Part A and B1, 2, 3, 4, and 5 (cont.)

- 7. The auto-antibody panel will be assessed at Screening, pre-dose Cycles 3 and 9, and every 6 cycles thereafter. In participants who develop signs and/or symptoms suggestive of auto-immune disease while on-treatment, the auto-antibody panel (anti-nuclear antibody, anti-double-stranded deoxyribonucleic acid (DNA), circulating anti-neutrophil cytoplasmic antibody [cANCA], and perinuclear anti neutrophil cytoplasmic antibody [pANCA]) should be repeated. Patients with confirmed positive serology of at least one of the auto-antibody panel during the course of the study should be discussed between Sponsor and Investigators, and if judged clinically relevant, could be referred to a specialist to exclude an underlying auto-immune disease.
- 8. Serology (as per local regulations) includes HIV, hepatitis B surface antigen, total hepatitis B core antibody, hepatitis C virus antibody. Results must be obtained and reviewed prior to administration of RO7121661.
- 9. Coagulation sampling (including prothrombin time [PT], international normalized ratio [INR], and activated partial prothrombin time [aPTT]) will be performed at the specified time-points (prior to dosing). After Cycle 6, coagulation sampling will be performed at every visit when tumor assessment is performed. Additional coagulation parameters (i.e., anti-thrombin III, fibrinogen, PT, fibrin degradation products, D-dimer) maybe be assessed according to clinical judgment.

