Tumor assessment will be performed at the time points described in the SoA (Section 1.3). All tumor assessments after baseline may be done within ± 7 days of the scheduled visit. Confirmation of objective responses (partial and complete responses) will be done at the next scheduled visit after at least 28 days from the initial response. If disease progression is determined solely by symptomatic deterioration, a RECIST Tumor Assessment eForms must be completed at that time indicating disease progression. At the Investigator's discretion, CT scans may be repeated at any time if progressive disease is suspected.

8.1.2 Photography of Cutaneous Lesions

Cutaneous lesions not evaluable by CT or MRI will be documented by color digital photography, including a ruler to estimate lesion size. Cutaneous lesions may be considered target lesions if they meet RECIST 1.1 criteria (see Appendix 7), otherwise they may be considered non-target lesions.

Photographs of cutaneous lesions will be taken at screening and on the same day as tumor assessment visit or at the first clinic visit following each tumor assessment.

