9.3 POPULATIONS FOR ANALYSES

For purposes of analysis, the following populations are defined in Table 7.

Table 7 Analysis Populations

Population	Description
Dose Limiting Toxicity	The DLT-evaluable population is defined as all participants who received at least two doses of study medication and either:
	experienced a DLT within the DLT period OR
	cleared the DLT period without a DLT
	The DLT period is 21 (Q2W) from Day 1/Cycle 1 to Day 7/Cycle 2. If there is a delay in Cycle 2 treatment the DLT period should be adjusted to cover Day 7/Cycle 2 up to a maximum of 35 (Q2W) days, since the maximum dose delay allowed is 14 days.
Efficacy	All participants in the safety population who received at least one dose of study drug and who have at least one baseline and one on-study tumor assessment. Participants who received at least one dose of study drug and discontinued the study because of progression before the first on-study tumor assessment will be considered as response-evaluable.
Safety	All participants who received at least one dose of the study treatment, whether prematurely withdrawn from the study or not, will be included in the safety analysis. Unless otherwise specified, the safety population will be the default analysis set used for all analyses.
Pharmacokinetic	All participants who have received at least one dose of study treatment and who have data from at least one post-dose sample will be included in the PK analysis population. Participants will be excluded from the PK analysis population if they significantly violate the inclusion or exclusion criteria, deviate significantly from the protocol, or if data are unavailable or incomplete which may influence the PK analysis. Excluded cases will be documented together with the reason for exclusion. All decisions on exclusions from the analysis will be made prior to database closure.

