9.4.2 Efficacy Analyses

The primary and secondary efficacy analyses listed in Table 8 will include all participants in the efficacy population with participants grouped according to dose cohort within each study part.

Table 8 Efficacy Statistical Analysis Methods

Endpoint	Statistical Analysis Methods
According to RECIST Version 1.1 criteria and iRECIST:	No formal statistical model and no formal hypothesis testing are planned in this study. Tumor response data will be reported using descriptive statistics. Response data will be listed. ORR and DCR will be summarized by using relative frequencies and 90% confidence interval (CI). If data are sufficient, duration of response and PFS will be summarized by using time-to-event analyses and Kaplan-Meier curves. The above analyses will be carried out for RECIST Version 1.1 (primary analysis) and iRECIST (exploratory analysis).
Overall Survival (OS)	OS data may be tabulated and summarized using time-to-event analyses and Kaplan-Meier curves if data is collected and mature.
	Eventually, summaries will be carried out by cohort separately for each part.

Objective response rate (ORR) and disease control rate (DCR) are determined as the rate of participants with an objective tumor response of CR or partial response (PR) (ORR) or CR, PR or stable disease [SD] (DCR). For this protocol, confirmation of response is required at least 4 weeks after a first response occurred. To classify a response as SD, measurements will have to be classified as stable (according to RECIST Version 1.1) at least once at a minimum of 4 weeks after study entry.

In the primary analysis ORR and DCR will be derived for RECIST Version 1.1 and will be based on Investigators' assessment. Participants with missing or no response assessments will be classified as not evaluable unless there is documented clinical deterioration, in which case participant will be classified as non-responders.

DoR will be calculated for participants who have a best (confirmed) overall response of CR or PR and will be defined as the time from first occurrence of a documented response until the time of documented disease progression or death (death within 30 days from last study treatment) from any cause, whichever occurs first. Censoring methods will be the same as the one applied for progression-free survival (PFS).

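### The efficacy population drops treated participants who leave or die of other causes before any on-study scan, so primary ORR, DCR and PFS can only be shifted upward

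*Combined protocol and SAP*

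**What the plan says.** Section 9.4.2 names the analysis set: "The primary and secondary efficacy analyses listed in Table 8 will include all participants in the efficacy population". Table 7 in Section 9.3 defines that set as members of the safety population "who received at least one dose of study drug and who have at least one baseline and one on-study tumor assessment". It has one exception: those who "discontinued the study because of progression before the first on-study tumor assessment will be considered as response-evaluable".

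Table 7 also has a default: "Unless otherwise specified, the safety population will be the default analysis set used for all analyses". Because Section 9.4.2 specifies another set for efficacy, the default does not apply there.

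Section 9.4.2 then adds a rule for ORR and DCR: "Participants with missing or no response assessments will be classified as not evaluable unless there is documented clinical deterioration". Where such deterioration is on record, the outcome differs: "in which case participant will be classified as non-responders". It does not say whether a not-evaluable participant counts in the denominator.

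PFS is defined in Section 3 (Table 4) and in Section 9.4.2 with death from any cause as an event. Participants with neither event are censored at their last tumor assessment. On timing, Table 1 footnote 6 in Section 1.3 says: "Measurable lesions will be assessed at Screening and then every 8 weeks", with a window of 7 days either side.

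**The concern.** ORR, DCR and PFS are primary endpoints for the Part B expansion cohorts, and the same set governs the secondary efficacy analyses in Part A. The first scheduled on-study scan comes seven to nine weeks after the first dose. A treated participant who dies of a non-progression cause, withdraws consent (after which Section 7.2 ends follow-up) or is lost in that window has no route into the analysis.

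This selection works in one direction. A person without an on-study assessment cannot be classed as CR, PR or SD, so removal shrinks the denominator and leaves the numerator unchanged. For PFS, the removed early deaths are events under the protocol's own definition.

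In a single-arm study without hypothesis tests, the estimate and its interval are the result. Section 9.5 also lets DCR or PFS weigh against a futility stop and names no analysis set for that comparison. If it uses the efficacy population, the same lift applies there.

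**Working it through.** **Figures in the plan.** There is no stated figure to reproduce: the plan gives no target rate, power or early-loss rate, and the cohort sizes are not shown. Cohort size, losses, responders and PFS level below are all assumptions.

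**Who falls where, if treated but without an on-study assessment**

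| Situation | Table 7 | Section 9.4.2 response rule |
|---|---|---|
| Left because of progression | In the set | Non-responder if deterioration is documented, otherwise not evaluable |
| Documented deterioration, left for another reason | Absent | Non-responder |
| Non-progression death, withdrawal or loss, no deterioration documented | Absent | Not evaluable |

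The second row is the direct conflict. It is narrow, because Section 8.1.1 adds: "If disease progression is determined solely by symptomatic deterioration, a RECIST Tumor Assessment eForms must be completed at that time indicating disease progression".

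**ORR and DCR factor.** With n treated, k dropped, x responders (or disease-controlled) and d = k/n, the ratio is [x/(n-k)] / [x/n] = 1/(1-d).

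- d = 5%: 1/0.95 = 1.05
- d = 10%: 1/0.90 = 1.11
- d = 15%: 1/0.85 = 1.18

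**Illustration.** Assume 40 treated, 4 never scanned, and 2 more scanned but not evaluable. Intervals are exact (Clopper-Pearson) 90%.

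| Denominator | ORR, 6 responders | DCR, 16 controlled | Upper limit, 0 responders |
|---|---|---|---|
| All treated, 40 (benchmark, not in the plan) | 15.0% (6.7 to 27.5) | 40.0% (26.9 to 54.2) | 7.2% |
| Table 7 set, 36 | 16.7% (7.5 to 30.3) | 44.4% (30.2 to 59.4) | 8.0% |
| Table 7 set less not evaluable, 34 | 17.6% (8.0 to 31.9) | 47.1% (32.2 to 62.3) | 8.4% |

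The last two rows differ only because the plan is silent on not-evaluable participants inside the set. With no responders, ORR is 0% on every row, so the zero-response futility trigger does not move. DoR uses confirmed responders only and does not move either.

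**PFS.** Let e be the share of treated participants who are excluded early non-progression deaths, and w the share who leave alive and unscanned. If the latter are censored at Day 1 and there is no other early censoring, S_set = S_all / (1 - e/(1-w)). For an assumed all-treated 6-month PFS of 25.0%:

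- e = 2.5%, w = 0: 0.25/0.975 = 25.6%
- e = 5%, w = 0: 0.25/0.95 = 26.3%
- e = 5%, w = 5%: 0.25/(1 - 0.05/0.95) = 26.4%
- e = 0, w = 10%: 25.0%

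So early deaths move the curve and live leavers do not. As a stress case, take 40 treated with 12 other events and 4 excluded deaths by week 8. PFS at week 8 is 24/40 = 60.0% on all treated and 24/36 = 66.7% on the Table 7 set. That requires 10% early non-progression deaths.

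**Censoring gap.** For someone with no post-baseline scan, the last tumor assessment is the screening scan, which precedes Day 1. An all-treated PFS analysis therefore needs an explicit rule.

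**The case against.** The strongest reply is that a response-evaluable set is a deliberate, pre-specified choice for preliminary activity in a Phase 1 expansion, in a study that claims no hypotheses, power or formal tests. Several parts of it stand.

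- A reader might infer that the text leaves the denominator open among all treated, the Table 7 set, and that set less the not evaluable. The documents do not support this. Section 9.4.2 specifies the efficacy population, so all treated is not one of its readings. The only open point is the status of not-evaluable participants within the set. Even there, Appendix 7 (Table 3) treats NE as a best-response category, which favors keeping them in.
- A reader might infer a general contradiction between Table 7 and the response rule. The rule has a coherent role inside the set, for unreadable scans and for those who left with progression. Only the narrow group shown above is treated inconsistently.
- A reader might infer that everyone who stops drug for toxicity is lost. Footnote 6 continues imaging to the later of progression and treatment discontinuation, so stopping drug does not by itself end scanning. Anyone scanned stays in.
- All-treated ORR and DCR can be rebuilt exactly, because the numerator is unchanged and the safety population is summarized by cohort (Section 9.4.1). PFS cannot be rebuilt this way.

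None of this removes the exclusion or its one-sided direction.

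**Conclusion.** The concern holds as a stated rule that can bias primary estimates upward, at minor to moderate severity. ORR and DCR rise by 1/(1-d) whenever someone is dropped and the numerator is not zero, and early non-progression deaths are lost from PFS.

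For an assumed 5% to 15% dropped, the relative increase in ORR and DCR is 5% to 18%. In the illustration, moving from all treated to the Table 7 set adds 1.7 percentage points to ORR and 4.4 to DCR, against 90% intervals about 21 and 27 points wide. With up to 5% early non-progression deaths, the assumed 6-month PFS rises by no more than 1.4 points. The life-expectancy criterion of at least 12 weeks suggests such deaths will be few. If nobody is dropped, nothing changes.

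The direction follows from the text. The size rests entirely on assumed inputs. The documents do not support calling this an error-rate problem.

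**What to change.** In Sections 9.3 and 9.4.2:

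- Make all treated participants (the safety population) the primary set for ORR, DCR and PFS.
- Replace the not-evaluable sentence: participants with no assessment supporting CR, PR or SD stay in the denominator as non-responders and as not disease-controlled.
- Count every death as a PFS event. Censor at Day 1 anyone with no post-baseline scan and no death.
- Keep the current efficacy population as a sensitivity analysis, and report by cohort how many were excluded and why.

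Name the same set in Section 9.5 for any DCR or PFS comparison.

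The cost is wording; no new data are needed. Reported rates will be slightly lower, and comparison with studies reported on response-evaluable sets less direct. The sensitivity analysis covers the latter.

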9.4 STATISTICAL ANALYSES

9.4.1 Demographics and Baseline Characteristics

Demography and baseline characteristics (including age, sex, participant disposition, previous therapies, and medical history) will be analyzed using descriptive statistics. The analysis will be based on the safety analysis population. Data will be summarized by dose cohort and regimen within each part.

9.4.2 Efficacy Analyses

The primary and secondary efficacy analyses listed in Table 8 will include all participants in the efficacy population with participants grouped according to dose cohort within each study part.

Table 8 Efficacy Statistical Analysis Methods

Endpoint	Statistical Analysis Methods
According to RECIST Version 1.1 criteria and iRECIST:	No formal statistical model and no formal hypothesis testing are planned in this study. Tumor response data will be reported using descriptive statistics. Response data will be listed. ORR and DCR will be summarized by using relative frequencies and 90% confidence interval (CI). If data are sufficient, duration of response and PFS will be summarized by using time-to-event analyses and Kaplan-Meier curves. The above analyses will be carried out for RECIST Version 1.1 (primary analysis) and iRECIST (exploratory analysis).
Overall Survival (OS)	OS data may be tabulated and summarized using time-to-event analyses and Kaplan-Meier curves if data is collected and mature.
	Eventually, summaries will be carried out by cohort separately for each part.

Objective response rate (ORR) and disease control rate (DCR) are determined as the rate of participants with an objective tumor response of CR or partial response (PR) (ORR) or CR, PR or stable disease [SD] (DCR). For this protocol, confirmation of response is required at least 4 weeks after a first response occurred. To classify a response as SD, measurements will have to be classified as stable (according to RECIST Version 1.1) at least once at a minimum of 4 weeks after study entry.

In the primary analysis ORR and DCR will be derived for RECIST Version 1.1 and will be based on Investigators' assessment. Participants with missing or no response assessments will be classified as not evaluable unless there is documented clinical deterioration, in which case participant will be classified as non-responders.

DoR will be calculated for participants who have a best (confirmed) overall response of CR or PR and will be defined as the time from first occurrence of a documented response until the time of documented disease progression or death (death within 30 days from last study treatment) from any cause, whichever occurs first. Censoring methods will be the same as the one applied for progression-free survival (PFS).

PFS will be defined as the time from study treatment initiation (Cycle 1 Day 1) to the first occurrence of documented disease progression (based on RECIST Version 1.1 Investigator's assessment) or death from any cause, whichever occurs first. For

participants who do not have documented progressive disease or death during the study, PFS will be censored at the day of the last tumor assessment.

Sensitivity analyses of response endpoints (ORR, DRC, DoR, and PFS) may include the evaluation of response according to iRECIST.

OS is defined as the time from the first dose of study treatment to the time of death from any cause. Participants who are still alive at the time of analysis will be censored at the time of their last study assessment (for active participants) or at the last date known alive (for participants in follow-up).

9.4.3 Safety Analyses

Unless otherwise specified all safety analyses listed in Table 9 will be based on the safety population. All safety parameters will be analyzed using descriptive statistics, summarized and presented in tables. Data will be summarized by dose and regimen (if applicable) within each part.

Safety will be assessed through summaries of DLTs (for Part A), adverse events, changes in laboratory test results, changes in vital signs and ECGs, and exposure to study treatment.

Table 9 Safety Statistical Analysis Methods

Endpoint	Statistical Analysis Methods
AEs	The original terms recorded on the eCRF by the Investigator for AEs will be coded by the Sponsor.
	For classification purposes, preferred terms will be assigned by the Sponsor to the original terms entered on the eCRF, using the most up-to-date version of the MedDRA terminology for AEs and diseases. AEs will be graded according to NCI CTCAE grades v5.0.
	Adverse events will be summarized by mapped term and appropriate thesaurus level. Toxicity grade, seriousness, and relationship to study treatment will be presented, as well as summaries of deaths, AEs leading to death and premature withdrawal from study treatment. Glossary of AEs, medication, and procedures will be provided.
Nature and frequency of DLTs	DLT events will be presented by individual listings. The MTD will be estimated with a mCRM–EWOC using DLT-evaluable participants. The MTD estimate will be presented along with 90% Credible Intervals.
Clinical laboratory tests	All clinical laboratory data will be stored on the database in the units in which they were reported. Laboratory test values will be presented in International System of Units (SI units; Système International d'Unités) by individual listings with flagging of abnormal results.
	Shifts in NCI CTCAE v5.0 grades from baseline to the worst grade observed during treatment and summary tables of change from baseline over time based on SI (Standard International) units will be presented for selected laboratory parameters. Individual participant listings (abnormal values or out of range) will be produced. See Appendix 4 for details on standard reference ranges and data transformation and the definition of laboratory abnormalities. Additional figures/tables/listings will be produced as deemed appropriate.
Vital signs	Vital signs data will be presented by individual listings with flagging of values outside the normal ranges and flagging of abnormalities. In addition, tabular summaries will be used, as appropriate.
ECG data analysis	Abnormal ECG data will be presented by individual listings. In addition, tabular summaries will be used, as appropriate.
Concomitant medications	The original terms recorded on the participants' eCRF by the Investigator for concomitant medications will be standardized by the Sponsor by assigning preferred terms. Concomitant medications will be presented in summary tables and listings, as appropriate.
Exposure to study medication	Exposure to study medication will be summarized by total duration of study medication, number of cycles started, and cumulative dose using descriptive statistics. Dose interruptions and their reasons will be presented by dose level.

AE = adverse event; DLT = dose-limiting toxicity; ECG = electrocardiogram; eCRF = electronic cases report form; EWOC = Escalation with overdose control; mCRM = modified Continuous Reassessment Method; MedDRA = Medical Dictionary for Regulatory Activities; MTD = maximum tolerated dose; NCI CTCAE = National Cancer Institute Common Terminology Criteria for Adverse Events.

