3. OBJECTIVES AND ENDPOINTS

The objectives and corresponding endpoints provided in Table 4, apply to:

- Part A: RO7121661 single agent dose escalation phase
- Part B: RO7121661 single agent expansion in selected indications

Table 4 Objectives and Endpoints

Objectives	Endpoints
Primary	
Dose Escalation: Safety, tolerability, MTD and/or RDE.	 Nature and frequency of DLTs and other AEs, PD and PK profile.
	 Incidence, nature and severity of AEs graded according to the National Cancer Institute (NCI) Common Terminology Criteria for Adverse Events (CTCAE) v5.0.
Expansion: Assessment of the anti-tumor activity of RO7121661.	 According to Response Evaluation Criteria in Solid Tumors (RECIST) Version 1.1 criteria:
	 Objective response rate (ORR).
	 Disease control rate (DCR); defined as ORR+stable disease rate (SDR).
	 Duration of response (DoR).
	 Progression free survival (PFS) defined as the time from the first study treatment (Day 1) to the first occurrence of progression per Investigator assessment or death from any cause, whichever occurs first.
Secondary	
To characterize the immunogenicity profile of RO7121661 (Part A and B).	Incidence of anti-drug antibodies (ADAs).
To explore potential PD-1, TIM-3 and PD-1/TIM-3 specific PD biomarkers (Part B).	 Examine the profile and status of T cell proliferation/activation in tumor biopsies and peripheral blood.
To investigate the single and multiple dose PK of RO7121661 (Part A and B).	 PK profiles and parameters derived for RO7121661.
To explore degree of target binding of RO7121661 (in association with PK/PD) via RO (Part A).	Evaluate RO via ex-vivo assay.
To evaluate the safety and tolerability of RO7121661 (Part B).	 Incidence, nature and severity of AEs graded according to the NCI CTCAE v5.0.
To explore preliminary anti-tumor activity of RO7121661 (Part A).	 According to RECIST Version 1.1 criteria: Objective response rate (ORR).
	 Disease control rate (DCR).
	 Progression-free survival (PFS).
	 Duration of response (DoR).

Table 4 Objectives and Endpoints (cont.)

Objectives	Endpoints
Tertiary/Exploratory	
To make a preliminary assessment of the anti-tumor activity of RO7121661 using immune-related RECIST (iRECIST) (Part A and B).	 Investigator-determined assessment using iRECIST:
	o ORR.
	 DCR; defined as response rate (RR)+stable disease (SD).
	o DoR.

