If in the judgment of the Investigator, the participant is likely to derive clinical benefit from RO7121661 after a hold of more than 2 doses, study drug may be re-started.

If an IRR develops, the infusion of RO7121161 should be slowed down or interrupted. The participant should be monitored until complete resolution of the symptoms and treated as clinically indicated. Treatment or concomitant medication may include acetaminophen/paracetamol, antihistamine, IV saline, oxygen, bronchodilators, corticosteroids, and vasopressors, depending on the symptoms (see Section 8.3.8). Study treatment should be re-started as soon as medically justified in the opinion of the Investigator.

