7.1.2 Resumption of Study Treatment

If a participant has a complete response (CR) or achieves maximum clinical benefit as determined by the Investigator and the Sponsor after an integrated assessment of radiographic data, biopsy results (if available), and clinical status, the study treatment

may be paused at the discretion of the treating physician after *discussion* with the Medical Monitor. The participant may remain on study and be followed according to the SoA (Section 1.3). If the disease relapses or progresses, the study treatment may be resumed after consultation with the Medical Monitor.

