2.6.2 Duration of overall response

The duration of overall response is measured from the time measurement criteria are first met for CR/PR (whichever is first recorded) until the first date that recurrent or progressive disease is objectively documented (taking as reference for progressive disease the smallest measurements recorded on study).

The duration of overall complete response is measured from the time measurement criteria are first met for CR until the first date that recurrent disease is objectively documented.

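### DoR counts a death only within 30 days of last treatment while PFS counts any death, so a responder's later death without documented progression is in practice censored and DoR can be overstated (minor)

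*Combined protocol and SAP*

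**What the plan says.** Section 9.4.2 calculates DoR for participants with a confirmed CR or PR, from first documented response "until the time of documented disease progression or death (death within 30 days from last study treatment) from any cause, whichever occurs first". On censoring it adds only: "Censoring methods will be the same as the one applied for progression-free survival".

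For PFS, Table 4 in Section 3 uses the "first occurrence of progression per Investigator assessment or death from any cause, whichever occurs first", and Section 9.4.2 repeats this without a 30-day limit. The PFS censoring rule reads: "participants who do not have documented progressive disease or death during the study, PFS will be censored at the day of the last tumor assessment".

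No other section sets a competing DoR rule. Table 4 lists DoR without defining it. Appendix 7, Section 2.6.2, runs duration of response "until the first date that recurrent or progressive disease is objectively documented" and does not mention death. The plan gives no reason for the 30 days. The figure matches neither the adverse event reporting period of 60 days (Part A) or 90 days (Part B) in Section 8.3.1 nor the survival follow-up in Section 8.10.4.2.

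**The concern.** Two endpoints meant to describe the same responders treat the same death differently. A responder who dies more than 30 days after the last dose without documented progression ends PFS but not DoR. If that person is censored at the last scan, follow-up is cut because of the death. Kaplan-Meier then assumes that the person would have gone on responding like those still under observation, and the curve sits too high.

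DoR is an endpoint of Part B's primary objective (Table 4). Section 9.5 also names it among the endpoints that may overrule a non-binding futility result. An overstated DoR, or one that disagrees with PFS in the same people, could enter that judgement.

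**Working it through.** **1. Can the case arise?** Dosing is every 14 days, and Table 1, footnote 6, continues imaging "until disease progression or treatment discontinuation (whichever occurs last), initiation of a new line of therapy or death". Most responders will therefore be on drug or under scanning. A responder can still be off drug for more than 30 days:
- After CR or maximum benefit, treatment "may be paused at the discretion of the treating physician" (Section 7.1.2).
- Section 7.1.1 allows that "after a hold of more than 2 doses, study drug may be re-started".
- Appendix 6, Table 1, provides for toxicity holds of up to 12 weeks, or longer.
- Imaging stops at a new line of therapy.

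The group is narrow but not empty.

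**2. Which rule applies to the late death?** The PFS censoring sentence covers people with neither progression nor death. Read literally, the late death is neither a DoR event nor expressly censored. Censoring at the last scan is the practical reading.

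**3. Hand example (invented data, weeks).** Eight responders: progression at 16, 24, 32, 48 and 56; late deaths without progression at 28 (last scan 24) and 44 (last scan 40); one ongoing at 64.
- Every death counted: S = 7/8, 6/8, 5/8, 4/8 at weeks 16, 24, 28, 32. The median is 32.
- Late deaths censored at the last scan: S(16) = 7/8; S(24) = 7/8 × 6/7 = 0.75; S(32) = 0.75 × 4/5 = 0.60; S(48) = 0.60 × 2/3 = 0.40. The median is 48.

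This shows the mechanism, not a forecast.

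**4. Simulation.** The plan states no DoR figure to reproduce. From the plan: scans every 8 weeks in the first year, then every 12 weeks, each ±7 days. Assumed: response first seen at the first scan, exponential duration with true median 10 months, follow-up uniform over 6 to 24 months from response, and a given share of response endings being late death without documented progression. Each case has 400,000 responders. Results are 12-month Kaplan-Meier DoR; differences are taken from the rounded values.

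| Late-death share | Every death counted | Current rule | Difference (points) |
|---|---|---|---|
| 0% | .458 | .458 | 0 |
| 3% | .458 | .468 | 1.0 |
| 5% | .457 | .475 | 1.8 |
| 10% | .455 | .491 | 3.6 |
| 20% | .452 | .528 | 7.6 |

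At a 10% share, a true median of 6 months gives .272 against .306 (3.4 points), and 15 months gives .590 against .622 (3.2 points). The shift in the median depends on the scan grid, so no median figure is claimed.

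**5. What if scanning stops before the response ends?** Here 10% of responders have no scan after response truly ends and die after a gap. The benchmark is full scanning.

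| Gap to death (months) | Benchmark | Any-death rule | Current rule | Excess, any-death / current (points) |
|---|---|---|---|---|
| 3–9 | .458 | .474 | .490 | 1.6 / 3.2 |
| 6–12 | .459 | .488 | .491 | 2.9 / 3.2 |
| 9–15 | .460 | .499 | .492 | 3.9 / 3.2 |

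With follow-up of 12 to 48 months, the order already reverses at a gap of 6–12 months (3.3 against 3.2 points).

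**The case against.** **The any-death rule has its own bias.** Table 1 stops imaging at a new therapy, while Section 8.10.4.2 follows survival to 24 or 48 months. A responder who changes therapy and dies a year later would count as event-free until death. This stands. A reader might infer that counting every death can only improve DoR; the 9–15 month row shows otherwise. It is why the second sensitivity analysis is needed.

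**The exposed group is smaller than it looks.** Section 8.1.1 requires progression judged solely on symptomatic deterioration to be entered as progression on the tumor assessment form, and it allows CT at any time on suspicion. Many declining responders would therefore have documented progression before death. This stands, although Appendix 7 does not treat symptomatic deterioration as an objective response status.

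**PFS is not wholly free of limits.** Its censoring sentence refers to death during the study. Survival follow-up is headed as post-study in Section 8.10.4.2 but listed within study duration in Section 4.1.1. This also stands, so the fix must settle the point for both endpoints.

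**Few patients are involved.** Cohort sizes are redacted. Assuming 20 to 60 per cohort and an ORR of 5 to 20% gives 20 × 0.05 = 1 to 60 × 0.20 = 12 responders. At a 10% share, 6.3% of simulated responders had an observed late death, so 0.06 to 0.76 such deaths are expected per cohort. The usual effect is nil. This lowers the severity but leaves the rule unexplained.

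**Conclusion.** The inconsistency is real and of minor severity. DoR and PFS handle a late death differently without a stated reason, and the practical handling for DoR is informative censoring. The overstatement is about 2 to 8 points at 12 months for assumed late-death shares of 5 to 20%. That size requires deaths to occur while scanning is ongoing or soon after it stops, and it is zero when there are none.

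Three stronger readings are not supported:
- **A contradiction with another DoR rule.** Table 4 defines none, and Appendix 7 is silent on death.
- **An explicit instruction to censor late deaths at the last scan.** The borrowed sentence does not reach them.
- **Damage to error rates or to the stated stopping rule.** Sections 9.1 and 9.2 set no hypothesis, alpha or power. Kaplan-Meier is used only if data are sufficient, and responses are also listed. The rule in Section 9.5 turns on zero responses, when no DoR exists.

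**What to change.** Remove the parenthetical 30-day limit in Section 9.4.2. Suggested wording: *DoR runs from the first documented response to the earlier of documented progression and death from any cause; responders with neither are censored on the date of their last tumor assessment.* Apply it to RECIST 1.1 and iRECIST alike.

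State once, for both DoR and PFS, whether deaths known only from survival follow-up count as occurring during the study.

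Add two labelled sensitivity analyses:
1. The present 30-day version.
2. Censoring at the last tumor assessment before new anti-cancer therapy, or before two or more consecutive missed assessments.

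**Cost.** This is a short text change and two extra analyses, with no new data. Survival status (Section 8.10.4.2), deaths after the adverse event reporting period (Appendix 2, Section 5.1) and post-study therapies (Table 1, footnote 13) are already collected.

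**Downsides.** Reported DoR may be slightly shorter. When death comes roughly 9 months or more after response truly ends without a scan, or somewhat sooner with long follow-up, the any-death rule overstates DoR slightly more than the present one; the second sensitivity analysis would show this. Late deaths remain unknown beyond survival follow-up or after consent is withdrawn (Section 7.2).
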